[name], Research Associate, has experience working with communities which lack access to needed resources here and abroad. He will oversee the design and implementation of data collection in REDCap as well as aid in data analysis.

[name], Research Associate, has experience in providing research support from development to implementation and dissemination. She will aid in program implementation at the Fort Apache site.

- 3. How will non-professional personnel (data collectors) involved with the data collection and analysis be trained in human subjects research ethical protections? (Use the JHSPH Ethics Field Training Guide available on the JHSPH IRB website. If the study is a clinical trial, consider using the JHSPH Good Clinical Practice (GCP) For Social and Behavioral Research Field Guide).
 - All study staff are trained and certified in human subjects confidentiality, HIPAA compliancy and GCP for Social and Behavioral Research as part of their onboarding process when hired; and safe conduct of research during COVID-19. Initial training in all study procedures will be conducted by the PI virtually and include role-playing. Investigators will provide weekly Zoom supervision. There will be daily supervision provided at each local site by site team leads, with additional in-person oversight by co-Is. All levels of training and supervision will target that study staff satisfactorily administer the intervention and survey.
- 4. If the JHSPH PI is responsible for data collection and will not personally be on-site throughout the data collection process, provide details about PI site visits, the supervision over consent and data collection, and the communication plan between the PI and study team.

Investigators will provide weekly Zoom supervision. There will be daily supervision provided at the local site by site team leads and/or site supervisors, who will be in regular contact with the study manager and Pls.

B. Protocol Compliance and Recordkeeping:

Describe how you plan to ensure that the study team follows the protocol and properly records and stores study data collection forms, IRB regulatory correspondence, and other study documentation. (For assistance, contact: [contact] Please provide information about study oversight to ensure compliance with IRB approval and regulatory and institutional requirements. If the study team does not follow study procedure, what is your plan for reporting protocol non-compliance?

All study staff will be managed and supervised by a local site team lead and/or site supervisor. This will involve regular debriefings with staff to review activities and identify any issues or challenges. In addition, consent and data collection forms and notes will be reviewed by the local site manager and study staff to ensure that study protocols are being properly adhered to. Any paper consent forms, data collection forms, and handwritten notes will be stored in a locked filing cabinet on site that will only be accessible by the local site managers. No data or forms will be accessed or allowed to be taken out of the room directly by anyone other than them. The site team lead/supervisor takes responsibility for collecting data records (forms and notes) from staff and ensuring that files are destroyed once the study is complete. The site team lead/supervisor will be in close communication with [name] to ensure these processes are adhered to. In the case of non-compliance, local site managers will inform [name] who will determine whether the non-compliance is serious and when to report it to the IRB.

C. Safety Monitoring:

1. Describe how participant safety will be monitored as the study progresses, by whom, and how often. Will there be a medical monitor on site? If yes, who will serve in that role and what is that person's specific charge?

The PI, [name], assumes responsibility for the safety of study participants. Study staff will be trained to monitor for the safety of study participants and report any concerns immediately to the site manager and the PI. Study staff will be trained in human subject's research and will be required to complete the CITI ethics module prior to any interaction with participants or study data. Certificates of human subject's completion will be kept on file at the Center for American Indian Health's office in Baltimore. A list of community resources will be provided with each assessment visit – either verbally by the study staff administering the survey or by paper.

At the end of any assessment administered, a notification will appear to the research program assistant if suicide risk (e.g., recent ideation and/or recent attempt) is indicated, the research program assistants will then respond in a graduated fashion based on the safety protocol outlined in 'Miscellaneous documents'.

- 2. If a Data Safety Monitoring Board (DSMB), or equivalent will be established, describe the following:
 - a. The DSMB membership, affiliation, and expertise. N/A
 - b. The charge or charter to the DSMB. N/A
 - c. Plans for providing DSMB reports to the IRB. N/A

IRB #00020570 +CiM/HSP research plan v7 14Nov2022 Pls: [name] (Faculty PI) & [name] (Navajo Community PI) 3. Describe plans for interim analysis and stopping rules, if any. None.

D. Reporting Unanticipated Problems/Adverse Events (AEs) to the IRB (all studies must complete this section):

NOTE: The IRB does not require PROMPT reporting of all AEs, only those that are unanticipated, pose risk of harm to participants or others, and are related to the study.

Anticipated AEs may be reported with the Continuing Review/Progress Report.

Describe your plan for reporting to the JHSPH IRB, local IRBs, and (if applicable) to the sponsor. Include your plan for government-mandated reporting of child abuse or illegal activity.

Study staff will immediately alert the site manager and PIs in the event of an adverse event or unanticipated problem. The PI, [name], and the Sr. Project Coordinator will report serious adverse events to all relevant IRBs if it is unanticipated, poses a risk of harm to participants or others, and is related to the study. If there is any suspected harm to self, others, or abuse reported during a study visit, the study staff will immediately report this information to the site manager and PI. The PI and the site manager will report this to appropriate Tribal or Law Enforcement Authorities. With experience from previous studies with the White Mountain Apache and Navajo Nation communities, the study team is knowledgeable of how to report this type of event without revealing study participation.

E. Other IRBs/Ethics Review Boards:

If other IRBs will review the research, provide the name of each IRB/ethics review board and its Federal Wide Assurance number, if it has one (available on OHRP's website at http://www.hhs.gov/ohrp/assurances). For federally funded studies, subrecipients MUST have a Federal Wide Assurance (FWA) number from the OHRP. The IRB overseeing the subrecipient should be registered with the OHRP. The JHSPH IRB will not have oversight responsibility for international subrecipients, and generally will not oversee data collection at external U.S. institutions Please contact [contact] with questions.

Table 8. Navajo Nation IRB Information

Non-JHSPH IRB/REC	FWA Number
Navajo Nation Human Research Review Board [name]; [contact]; [contact]	00008894

F. "Engaged" in Human Subjects Research:

For studies that involve collaboration with non-JHSPH institutions, complete the chart below by describing the collaboration and the roles and responsibilities of each partner, including the JHSPH investigator. This information helps us determine what IRB oversight is required for each party. Complete the chart for all multi-collaborator studies.

N/A

Insert collaborator names and FWA numbers, if available. Note who will be "engaged" in human subjects research by filling in the following table:

Table 9. Grant and Federal Wide Assurance

IRB #00020570 +CiM/HSP research plan v7 14Nov2022 Pls: [name] (Faculty PI) & [name] (Navajo Community PI)

	JHSPH	
For federally funded studies, collaborators' FWA	00000287	
Primary Grant/Contract Recipient	Х	
Grant/Contract Subrecipient		
Hiring Data Collectors		
Training Data Collectors		
Obtaining Informed Consent and/or Identifiable Data		
Accessing/Analyzing Identifiable Data		
Overseeing storage, access and use of biospecimens		

COMPLETE THE FOLLOWING SECTIONS WHEN RELEVANT TO YOUR STUDY:

XI. Secondary Data Analysis of Existing Data:

A. Study Design:

1. Describe your study design and methods. The study design must relate to your stated aims/objectives.

The study design and aims are the same as for the application described above (see Section I). Secondary data analysis will consist of linking participant information to data collected as part of the Project SafeSchools study (IRB No.: 14911).

2. Provide an estimated sample size and an explanation for that number.

Based on data collected so far, we have estimated 45% of adult caregivers (based on their mental health scores at baseline) and 7% of youth (based on both their parent-reported mental health scores at baselines and their age) in the Project SafeSchools study are eligible for participation. We project a total enrollment of N = 264 adult caregivers in the Project SafeSchools study who are also reporting on an index child, leading to an estimated N = 118 caregivers and N = 26 youth ages 11-16 (index children in the Project SafeSchools cohort study) who will have reported (either self- or parent-report) mental distress or recent suicidal ideation that places them in the risk category for more severe disorder and who will be eligible to join the +CiM/HSP study.

3. Provide a brief data analysis plan and a description of variables to be derived.

Data from Project SafeSchools (IRB No.: 14911) will be used to help in estimating the stability of psychosocial functioning prior to interventions as well as serve as a longer-term follow-up of the impact of interventions over time. For our primary Aim, estimating the effectiveness of +CiM/HSP, we will used mixed-effects models to compare symptom scores across arms with our main outcome time point to be analyzed based on the Wave 3 outcome time point in Project SafeSchools, estimated to be approximately 3-6 months after enrollment into +CiM/HSP. For Aim 2, we will use a within subjects design to measure differences in symptoms prior to starting the +CiM/HSP intervention components compared to after completion of the intervention components using the Project Safe Schools Wave 1, 2, and 3 data collection timepoints. This analysis will focus on the measures that are common to both the +CiM/HSP protocol and the Project SafeSchools data (e.g.,

IRB #00020570 +CiM/HSP research plan v7 14Nov2022

PIs: [name] (Faculty PI) & [name] (Navajo Community PI)

Adult self-report on depression and anxiety symptoms and caregiver report on strengths and difficulties, resilience items).

B. Participants:

1. Describe the subjects who provided the original data and the population from which they were drawn.

Study subjects are all youth ages 11-16 or adult caregivers over the age of 18 that either attend or have a student attending a school serving enrolled tribal members of the White Mountain Apache Tribe or the Navajo Nation.

Note: If you are receiving, accessing, or using data from a U.S. health care provider, the need for HIPAA review is likely. If you plan to bring identifiable health information from a foreign country to a U.S. covered entity (e.g., lab at the Hopkins SOM), HIPAA may be triggered. If either of these conditions is met, check "yes" to the HIPAA question in the PHIRST application.

2. If you plan to analyze human specimens or genetic/genomic data, provide details about the source of those specimens and whether they were collected using an informed consent document. If yes, explain whether your proposed use is "consistent with" the scope of the original consent, if it potentially introduces new analyses beyond the scope of the original consent, and/or if it introduces new sensitive topics (HIV/STDs, mental health, addiction) or cultural/community issues that may be controversial.

N/A

3. Explain whether (and how) you plan to return results to the participants either individually or as a group.

The results will be disseminated to all study participants through partnerships and presentations at board of director meetings, school board meetings, and public forums as deemed appropriate by local collaborators. Only de-identified data and analyzed in aggregate will be shared.

XII. Oversight Plan for Student-Initiated Studies:

A. For student-initiated studies, explain how the PI will monitor the student's adherence to the IRB-approved research plan, such as communication frequency and form, training, reporting requirements, and anticipated time frame for the research. Describe who will have direct oversight of the student for international studies if the PI will not personally be located at the study site, and their qualifications.

N/A

B. What is the data custody plan for student-initiated research? (Note: Students may not take identifiable information with them when they leave the institution.)

N/A

XIII. Creation of a Biospecimen Repository:

Explain the source of the biospecimens, if not described above, and what kinds of specimens will be retained over time. Clarify whether the specimens will be obtained specifically for repository purposes, or will be obtained as part of the core study and then retained in a repository.

A. Describe where the biospecimens will be stored and who will be responsible for them.

IRB #00020570 +CiM/HSP research plan v7 14Nov2022

Pls: [name] (Faculty PI) & [name] (Navajo Community PI)

N/A

B. Describe how long the biospecimens will be stored, and what will happen at the end of that period.

N/A

C. Explain whether the biospecimens will be shared with other investigators, inside and outside of JHU, how the decision to share will be made, and by whom. Include your plans, if any, for commercial use. Also explain how downstream use of the specimen will be managed, and what will happen to left-over specimens.

N/A

D. Describe whether future research using the biospecimens will include specimen derivation and processing (cell lines, DNA/RNA, etc.), genomic analyses, or any other work which could increase risk to participants. Explain what additional protections will be provided to participants.

N/A

E. If future research could yield unanticipated incidental findings (e.g., an unexpected finding with potential health importance that is not one of the aims of the study) for a participant, do you intend to disclose those findings to the study participant? Please explain your position.

N/A

F. Explain whether the specimens will be identifiable, and if so, how they will be coded, who will have access to the code, and whether the biospecimens will be shared in linked (identifiable) form.

N/A

G. Explain whether the repository will have Certificate of Confidentiality protections.

N/A

H. Explain whether a participant will be able to withdraw consent to use a biospecimen, and how the repository will handle a consent withdrawal request.

N/A

I. Describe data and/or specimen use agreements that will be required of users. Provide a copy of any usage agreement that you plan to execute with investigators who obtain biospecimens from you.

N/A

XIV. Data Coordinating Center:

Complete if JHSPH serves as the Data Coordinating Center.

A. How will the study procedures be developed?

N/A

IRB #00020570 +CiM/HSP research plan v7 14Nov2022

PIs: [name] (Faculty PI) & [name] (Navajo Community PI)

B. How will the study documents that require IRB approval at each local site be developed? Will there be some sort of steering or equivalent committee that will provide central review and approval of study documents, or will template consent forms, recruitment materials, data collection forms, etc. be developed by and provided to the local sites by the coordinating center without external review?

N/A

C. Will each local clinical site be overseen by its own IRB with an FWA, or will a Single IRB review the study? State whether the coordinating center will collect IRB approvals and renewals from the clinical centers; if not, explain why.

N/A

D. How will the coordinating center provide each local site with the most recent version of the protocol and other study documents? What will be the process for requesting that these updates be approved by local clinical center IRBs?

N/A

E. What is the plan for collecting data, managing the data, and protecting the data at the coordinating center?

N/A

F. What is the process for reporting and evaluating protocol events and deviations from the local sites? Who has overall responsibility for overseeing subject safety: the investigators at the recruitment site, the Coordinating Center, the Steering Committee, or a Data and Safety Monitoring Board (DSMB)? Is there a DSMB that will evaluate these reports and provide summaries of safety information to all the reviewing IRBs, including the coordinating center IRB? Please note that if there is a DSMB for the overall study, then the coordinating center Pl does not have to report to the coordinating center IRB each individual adverse event/problem event that is submitted by the local site Pls.

N/A

G. Some FDA regulated studies have different AE reporting criteria than that required by the IRB (IRB Policy No. 103.06). How will you reconcile the different requirements, and who is responsible for this reconciliation?

N/A

H. Who is responsible for compliance with the study protocol and procedures and how will the compliance of the local sites be monitored and reviewed? How will issues with compliance be remedied?

N/A

XV. Drug Products, Vitamins, Food and Dietary Supplements:

Complete this section if your study involves a drug, botanical, food, dietary supplement, or other product that will be applied, inhaled, ingested or otherwise absorbed by the study participants. If you will be administering drugs, please upload the product information.

N/A

A. List the name(s) of the study product(s), and the manufacturer/source of each product.

N/A

Name of Study Product	Manufacturer/Source

B. List each study product by name and indicate its approved/not approved status.

N/A

Approved by the FDA and Commercially Available	Approved by Another Gov't Entity (provide name)	Cleared for Use at Local Study Site

C. If your study product has an Investigational New Drug (IND) application through the U.S. Food and Drug Administration, provide the IND number, and the Investigators Brochure.

N/A

Who will hold the IND?

N/A

D. If your study product is a marketed drug, provide the package inserts or other product information. If the study product WILL NOT be used for its approved indication, dose, population, and route of administration, provide a detailed rationale justifying the off-label use of the study product.

N/A

E. If the study product does not require FDA approval (e.g., dietary supplements, botanicals, products not subject to the U.S. FDA, etc.), provide safety information (as applicable) and a certificate of analysis.

N/A

A. Explain who will be responsible for drug management and supply, labeling, dispensing, documentation, and recordkeeping. Complete and upload into PHIRST the Drug Data Sheet available on the JHSPH IRB website at www.jhsph.edu/irb.

N/A

B. What drug monitoring and/or regulatory oversight will be provided as part of the study? Please describe.

IRB #00020570 +CiM/HSP research plan v7 14Nov2022

PIs: [name] (Faculty PI) & [name] (Navajo Community PI)

N/A

XVI. Medical Devices:

Complete this section if your study will involve an approved or investigational medical device (**diagnostic**, non-significant risk, significant risk).

A. List the name(s) of the study product(s), the manufacturer/source of each product, and whether or not it is powered (electric, battery). Provide product information. If it is electric, upload documentation of clinical engineering approval or its equivalent from a local authority, to ensure that the device is in good working order.

N/A

Name of Study Product	Manufacturer/Source	Powered?

B. List each study product by name and indicate its status as approved by a government authority or not approved.

N/A

Approved by the FDA and Commercially Available	Approved by Another Gov't Entity (provide name and approval information)	Not Approved

C. If your investigational device is Exempt from the FDA IDE regulations, explain which section of the code applies to your device and why it meets the criteria provided. If it is a **diagnostic device**, provide preclinical information about the sensitivity and specificity of the test and the anticipated failure rate. If you plan to provide the results to participants or their physicians, justify doing so, and explain how those results will validated (or not) against the current "gold standard".

N/A

D. If you believe the investigational device is not IDE exempt under 21CFR 812.2(c) but is a "Non-Significant Risk" device considered to have an approved IDE application, provide information from the manufacturer supporting that position.

N/A

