We will conduct a Pilot Randomized Controlled Trial (RCT) among caregivers and youth (11-16 years old) who score at elevated risk of anxiety or depression. Participants will be recruited from the sample of individuals who have scored "at risk" on a mental health screening assessment tool in an ongoing cohort study, Project SafeSchools (IRB No.: 14911). All persons who screen "at risk" will be approached for this pilot study using our standardized recruitment script. Parent/Caregiver participants and youth participants may be enrolled separately. All potential study participants will be screened for eligibility after going through the consent/assent process. This is to confirm that potential participants are still presenting with elevated mental health scores at the start of enrollment. For parent/caregiver participants, the screening will utilize the same assessments as those used in the Project SafeSchools cohort study. All youth participants will complete a version of the brief screening tool as well. The screening tool plus a set of additional questions related to the interventions will be administered at 30 days post consent, and again at 90 days post consent to all participants. These additional assessments are needed to understand the immediate impact of the intervention approaches. Additional participant data from the Project SafeSchools study will be analyzed to better understand symptoms prior to the pilot study enrollment, and as a longer-term outcome assessment for the pilot study. If promising, the results of this study will inform a future fully powered study to test these interventions at scale.

B. Provide a sample size and a justification as to how you arrived at that number. If you use screening procedures to arrive at a final sample, distinguish the screening sample size from the enrolled sample size; a table may be helpful. For electronic survey studies involving online recruitment and survey completion: consider how you will set controls on how many people will join your study.

This is a pilot study. As such, our main study objectives are to pilot the intervention materials, and study procedures. Given that we will recruit from currently enrolled participants in the Project SafeSchools cohort study, our sample size is limited to the number of participants

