Describe the study participants and the population from which they will be drawn. Specify the inclusion and exclusion criteria. If you plan to include children, note their ages and whether you will include children in foster care or who are wards of the State. Note if the participants are particularly vulnerable in terms of cognitive limitations, education, legal migration status, incarceration, poverty, or some combination of factors.

A. Inclusion Criteria:

All participants must be parents/caregivers or index youth enrolled in Project SafeSchools.

Adult participants:

- Have elevated levels of mental distress as reported in a Project SafeSchools assessment.
- Agreement to be re-contacted for future research as part of their Project SafeSchools consent.
- Meeting symptom eligibility criteria as outlined in Table 2 at a screening assessment/baseline visit.

Youth participants:

- Are 11-16 years old
- Agreement from parent/caregiver to be re-contacted for future research from their Project SafeSchools consent form.
- Meeting symptom eligibility criteria based on a self-report screening assessment/baseline visit (outlined in Table 2).

For the inclusion criteria, mental distress is defined as meeting eligibility cutoff scores on the following instruments:

- Adult Participants
 - o General Distress (Kessler)
 - Anxiety (PROMIS)
 - Depression (CESDR-10)
 - o Recent Suicide Ideation (either CESDR-10 or Ideation Questionnaire)
- Youth Participants:
 - Depression (CESDR-10)
 - o Emotional Problems (SDQ Emotional Problems Subscale)
 - Anxiety (SCARED)
 - o Recent Ideation (Ideation question on CESDR-10 or ideation questionnaire)

Table 2. Mental Health Assessments and Eligibility Scores

Mental Health Assessment	Scale	Cut Off Scores for Eligibility
Adult screening tools		
Kessler (Stress)	0-24 scale	13+ is high risk
CESDR-10 (Depression)	0-30 scale	8+ is high risk
CESDR-10 (Recent Suicide Ideation)	0-4	1+ is high risk
PROMIS (Anxiety)	8-40 scale	17+ is high risk
Caregiver report screening tools*		
SDQ (Emotional symptoms)	0-10 scale	5+ is high risk
SCARED (Anxiety)	0 - 82 scale	25+ is high risk
Suicide Ideation	0-4	4 is high risk
Youth self-report		
CESDR-10 (Depression)	0- 30 scale	8+ is high risk
CESDR-10 (Recent Suicide Ideation)	0-4	1+ is high risk
SDQ (Emotional symptoms)	0 – 10 scale	6+ is high risk
SCARED (Anxiety)	0 - 82 scale	25+ is high Risk

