Analysis for all aims: Are planned statistical analysis will focus on the parent/caregiver surveys, given anticipation that sample sizes will be higher for this group. However, we will analyze the youth self-report descriptively. For adult outcomes, we will examine change over time on outcome measures and differences on these trajectories by study arm (Aim 1) or by timepoint (Aim 2). Additional analyses may also occur depending on guidance from our Community Advisory Boards. Every effort will be made to generate complete data; however, inevitably some data will be missing, and the methods recommended by Schafer and Graham (2002) will be used to evaluate missing data assumptions and guide the analyses. Based on the amount of missing data and evidence for a Missing At Random versus Missing Not At Random missing data mechanism, missingness will be addressed. The missing data approach will be finalized before the outcome analysis. Our analytic plan will also leverage data collected as part of their participation in the Project SafeSchools cohort study (see section XI for details). This will serve as a historical control comparison period for Aim 2, as well as provide a better understanding of longer-term impact of the interventions.

5. Answer the following **if they are relevant to your study design**:

A. If the study has different arms, explain the process for assigning participants (intervention/control, case/control), including the sequence and timing of the assignment.

Participants will be block randomized with blocking on age (e.g., caregiver vs. youth) and gender. A randomization table will be created in a statistical software (e.g., Stata, SAS, R) and incorporated into REDCap. Randomization and assignment of intervention or control groups will occur following consent by a study team member. The study team member will only need to select the randomization option within the participant's study REDCap form for randomization to occur.

B. If human biospecimens (blood, urine, saliva, etc.) will be collected, provide details about who will collect the specimen, the volume (ml) and frequency of collection, how the specimen will be used, stored, identified, and disposed of when the study is over. If specimens will be collected

for use in future research (beyond this study), complete the "Biospecimen Repository" section below.

N/A

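### Does Aim 1 leave its main adult test open between trajectories by arm and a Wave 3 comparison, with no role for the 90-day score?

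*Combined protocol and SAP*

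**What the plan says.** Section V.C.4, the brief analysis plan, says of adult outcomes: "we will examine change over time on outcome measures and differences on these trajectories by study arm (Aim 1"; the comparison by timepoint is assigned to Aim 2. It names no model and no main visit. It refers to section XI for the Project SafeSchools data, which it describes as the historical comparison for Aim 2, "as well as provide a better understanding of longer-term impact of the interventions". On missing data it says: "The missing data approach will be finalized before the outcome analysis".

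Section XI.A.3 gives the model and the time point for Aim 1. The model is a mixed-effects comparison of the two arms on symptom scores. The main visit is fixed by the words "with our main outcome time point to be analyzed based on the Wave 3 outcome time point in Project SafeSchools". The timing of that wave is given only as an estimate and not as a window: "estimated to be approximately 3-6 months after enrollment into +CiM/HSP".

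Section III.A separates the purposes. Of the 30- and 90-day surveys it says: "These additional assessments are needed to understand the immediate impact of the intervention approaches". The cohort data serve "as a longer-term outcome assessment for the pilot study". Table 5 lists the adult CESDR-10 and PROMIS at baseline, 30 days, 90 days and in the cohort data.

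Section III.B expects 75 analysable adults and a detectable effect of d = 0.66, with no visit attached. Section IV.A asks that adults "Have elevated levels of mental distress as reported in a Project SafeSchools assessment", without naming a wave.

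**The concern.** Read side by side, V.C.4 and XI.A.3 seem to promise two analyses of the same aim: a difference in trajectories and a difference at one later wave. The 90-day score falls around the end of the messages, on the same scales, yet no sentence gives it a place in the main estimate. Two costs could follow.

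- **Multiplicity.** The trial is unblinded. If a 90-day or trajectory result and a Wave 3 result could each be reported as the Aim 1 finding, there would be two chances of a positive result.
- **Precision.** With 75 adults, a second measure of each scale might be left out of the main estimate.

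Wave 3 is also scheduled by the cohort and not by randomisation, so some adults might have no Wave 3 score after randomisation. The 20% attrition allowance is not tied to a visit.

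**Working it through.** **The plan's own figure.** The inputs from III.B are 75 adults, equal allocation, alpha 0.05 and power 0.80. A two-sided two-sample t calculation gives d = 0.660 at 37 per arm and 0.656 at 37.5 per arm, against 0.66 stated. With the stated SDs, 0.66 × 6.4 = 4.2 (CESDR-10) and 0.66 × 5.3 = 3.5 (PROMIS), as in Table 1. The figure therefore describes a single-visit comparison, which agrees with a Wave 3 contrast.

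**Are the two sections incompatible?** A mixed model with arm, visit and their interaction describes trajectories by arm. Its arm difference at Wave 3 is the contrast that XI.A.3 calls main. Both sections are met by one model.

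**What does the unstated role of the 90-day score change?** Assume a correlation of 0.5 with baseline and r between follow-up scores; the documents give neither. Variances are in units of SD².

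- *Complete data.* With visit as a category and an unstructured covariance, the baseline-adjusted Wave 3 difference is identical with or without the earlier follow-up scores. Its standard error is 2 × √(0.75/75) = 0.20, where 0.75 = 1 − 0.5².
- *Wave 3 absent for 30% at random (assumed), leaving 52.5 of 75.* Without the interim scores: SE = 2 × √(0.75/52.5) = 0.239. With the 30- and 90-day scores at r = 0.7, their partial correlation with Wave 3 given baseline is (0.7 − 0.25)/0.75 = 0.6. Together they explain 2 × 0.6²/(1 + 0.6) = 0.45 of the remaining variance. SE = 2 × √(0.75 × (0.55/52.5 + 0.45/75)) = 0.222. The ratio is 0.239/0.222 = 1.08. At r = 0.5 the explained share is 0.167, the SE is 0.233 and the ratio is 1.03. Simulation at r = 0.7 gives about 0.228 with the interim scores and 0.243 without.

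**What would averaging day 90 and Wave 3 gain?** The variance factor is 0.75 for Wave 3 alone and (1 + r)/2 − 0.25 for the average. Detectable d = 0.656 × √factor.

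| | factor | d | CESDR-10 | PROMIS |
|---|---|---|---|---|
| Wave 3 alone | 0.75 | 0.57 | 3.6 | 3.0 |
| Average, r = 0.5 | 0.50 | 0.46 | 3.0 | 2.5 |
| Average, r = 0.7 | 0.60 | 0.51 | 3.25 | 2.7 |
| Average, r = 0.8 | 0.65 | 0.53 | 3.4 | 2.8 |

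This assumes the same effect at both times. The gain reverses if the 90-day effect is below 2 × √(factor/0.75) − 1 of the Wave 3 effect, which is 63%, 79% or 86% at r = 0.5, 0.7 or 0.8.

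**What if either test could count?** For two tests at 0.05 whose correlation is (r − 0.25)/0.75 = 0.33, 0.60 or 0.73, the chance of at least one false positive per scale is 0.095, 0.088 or 0.082. These rates apply only if the 90-day test may replace the named main time point.

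**The case for a change.** The strongest case for acting is that the plan never states the joint model. It has a directional effectiveness hypothesis and a powered effect size, so calling it a pilot does not remove the need for one fixed test. The 90-day data will be in hand anyway, and the averaged contrast is more precise over the range of correlations considered. The early edge of the Wave 3 estimate also overlaps the 90-day window.

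Part of this stands. The visits in the model, the Wave 3 window and the visit behind the attrition figure are not written down.

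The rest carries less weight. The false-positive rates require setting aside the time point that XI.A.3 calls main, while III.A gives the earlier surveys a different purpose, so an order of importance is already visible. The precision gain comes from changing the question to a blend of the effect near the end of the messages and a later one, which III.A keeps apart. It also depends on a constant effect. Where Wave 3 falls close to day 90, a high correlation is plausible and the gain is smallest: 0.57 to 0.53 at r = 0.8. Loss of Wave 3 scores may already be covered, since 75 is 94 less 20% attrition. XI.A.3 places Wave 3 after enrolment, and the cohort protocol, not available here, may settle the rest.

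**Conclusion.** No change is needed. The plan names a model class and one main time point for Aim 1, and the trajectory wording in V.C.4 fits the same model. Following it gives a valid randomised comparison at Wave 3. The silence on the 90-day score is a gap that an analyst fills in the ordinary way: the interim scores enter as repeated measures, the Wave 3 contrast is reported as main and the 90-day contrast as immediate impact. V.C.4 already provides a point before the outcome analysis at which such choices are settled.

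The choice of visits does not alter the Wave 3 estimate when data are complete. With 30% of Wave 3 scores absent, it alters the standard error by about 3% (r = 0.5) to 8% (r = 0.7). Averaging two visits is a fair alternative, worth 0.04 to 0.10 in detectable d under a constant effect, but it trades the later outcome for a mixed one, and reasonable statisticians would differ on it. All correlations and missing shares here are assumptions. The conclusion also assumes that Wave 3 is reported as the main result, as XI.A.3 says.
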